## 9.6. Warnings and Precautions

Special warnings or precautions for the study drug, derived from safety information collected by the sponsor or its designee, are presented in the Investigator Brochure. Additional safety information collected between IB updates will be communicated in the form of Investigator Notifications. Any important new safety information should be discussed with the participant during the study, as necessary. If new significant risks are identified, they will be added to the ICF.

## **9.7. Product Complaints**

The sponsor collects product complaints on study drugs and drug delivery systems used in clinical studies in order to ensure the safety of study participants, monitor quality, and facilitate process and product improvements.

All product complaints associated with material packaged, labeled, and released by the sponsor or its designee will be reported to the sponsor. All product complaints associated with other study material will be reported directly to the respective manufacturer.

The investigator or his/her designee is responsible for reporting a complete description of the product complaint via email or other written communication to the sponsor contact or respective manufacturer as noted in the packaging information. Any AE associated with a product complaint should be recorded as described in Section [9.3](#).

If the investigator is asked to return the product for investigation, he/she will return a copy of the product complaint communication with the product.

For Japan: Complaints associated with unapproved medical devices will be reported to the sponsor with a Medical Device Defect Report Form, and the sponsor will report medical device defects to the PMDA as per local regulatory requirements.

## **10. STATISTICS**

### **10.1. Sample Size Determination**

For Cohort A, approximately 60 participants are planned. Assuming the true ORR is 35% for the intervention in this group, 60 participants are needed to ensure that there is at least 90% power to test the null hypothesis of  $ORR \leq 15\%$ . This calculation assumes 1-sided test at the overall 0.025 level of significance.

For Cohort B, approximately 90 participants are planned. Assuming the true ORR is 30% for the intervention in this group, 90 participants are needed to endure that there is at least 90% power to test the null hypothesis of  $ORR \leq 15\%$ . This calculation assumes 1-sided test at the overall 0.025 level of significance.

For Cohort C, approximately 20 participants will be enrolled, which will provide at least 80% chance of observing at least 4 responders in this cohort if the underlying ORR is 30%.

### **10.2. Populations for Analysis**

Populations for analysis are shown in [Table 16](#).

**Table 16: Populations for Analysis**

Population	Description
Efficacy evaluable	
The efficacy evaluable population includes all enrolled participants in Cohorts A, B, and C who received at least 1 dose of study drug.
 
The efficacy evaluable population will be used for the summary of demographics, baseline characteristics, participant disposition, and analyses of all efficacy data.

Safety	The safety population includes all enrolled participants who received at least 1 dose of study drug. All safety analyses will be conducted using the safety population.
Per protocol	The per protocol population includes all efficacy evaluable population participants who are sufficiently compliant with the Protocol.
RECIST/RANO evaluable	
The RECIST/RANO evaluable population includes all efficacy evaluable population participants who have at least 2 objective tumor response assessments per independent centralized radiological review or who discontinued from the study or who discontinued from treatment without post-treatment tumor assessments.
 
RECIST/RANO evaluable population will be used for ORR analysis in the interim.

### **10.3. Level of Significance**

The overall level of significance is 1-sided 0.025. The primary endpoint in Cohort A and Cohort B will be tested sequentially at 1-sided 0.025. If ORR in Cohort A is significant, then ORR in Cohort B will be tested.

### **10.4. Statistical Analyses**

#### **10.4.1. Primary Analysis**

The primary endpoints of the study are ORR in Cohort A and Cohort B, respectively. Objective response rate is defined as the proportion of participants who achieved a CR or a PR based on RECIST v1.1 or RANO, as assessed by an independent centralized radiological review committee. This analysis will be based on efficacy evaluable population. Participants who do not have sufficient baseline or on-study response assessment information to be adequately assessed for response status will be included in the denominators in the calculation of ORR. The 95% CI for the ORR will be estimated using the Clopper-Pearson method. The p-value from the exact binomial test will be provided.

The ORR will also be analyzed based on the per protocol population as a sensitivity analysis.

#### **10.4.2. Secondary Efficacy Analysis**

Secondary efficacy analysis will be conducted for the efficacy evaluable population.

Progression-free survival is defined as the time from date of first dose of study drug to the earliest date of progressive disease or death, whichever is first. Progressive disease is evaluated based RECIST v1.1, or RANO, by the central radiographic review committee. Participants who are alive without progression before analysis cutoff date will be censored. Censoring for PFS will follow FDA guidance ([FDA 2017](#)). Progression-free survival data will be analyzed by the Kaplan-Meier method in Cohorts A and B, respectively.

For objective responders, DOR is defined as the time from the date that a participant first achieves CR or PR based on RECIST v1.1, or RANO, until the date of first documented disease progression based on RECIST v1.1, or RANO, or death. Participants who are alive without progression before analysis cut-off date will be censored. Censoring of DOR will follow the same algorithm as the censoring of PFS. Duration of response data will be analyzed by the Kaplan-Meier method in Cohorts A and B, respectively.

Overall survival is defined as the time from date of first dose of study drug to death due to any cause. Participants without death observed at the time of the analysis will be censored at last date known to be alive. Overall survival will be analyzed by the Kaplan-Meier method in Cohorts A and B, respectively.

#### **10.4.3. Safety Analyses**

[figure not shown]
Safety analyses will be conducted for the safety population. Adverse events will be coded by the MedDRA dictionary, and TEAEs (ie, AEs reported for the first time or worsening of a pre-existing event after first dose of study drug/treatment) will be tabulated by preferred term and system organ class for all events, related events, and events of Grade 3 or higher.

Quantitative safety variables and their changes from baseline (laboratory, vital signs, etc) will be summarized with descriptive statistics. Clinically notable abnormal values will be flagged and tabulated based on predefined criteria.

The clinical laboratory data will be analyzed using summary statistics; no formal treatment group comparisons are planned. In addition, distributions of key laboratory parameters may be plotted over time; these values will also be classified into CTCAE toxicity grades and tabulated. Descriptive statistics and mean change from baseline will be determined for vital signs at each assessment time. Vital sign results will be reviewed for clinically notable abnormalities.

Descriptive statistics and mean change from baseline will be determined for each ECG parameter at each assessment time. Electrocardiogram results will be reviewed for clinically notable abnormalities according to predefined criteria (see Section 8.3.4). Participants exhibiting clinically notable ECG abnormalities will be listed.

Measures of exposure of study drug will be summarized by means of summary statistics.

## **10.5. Interim Analysis**

For Cohort A, futility analysis will be performed when approximately 25 participants are enrolled into the cohort and have at least 2 objective tumor response assessments per independent centralized radiological review or are discontinued from the study or are discontinued from treatment without post-treatment tumor assessments. Cohort A can be stopped for futility if  $\leq 4$  responders are observed in RECIST/RANO evaluable population, for which there is  $< 10\%$  probability of claiming ORR  $> 15\%$  at final analysis. This rule is just a guidance and nonbinding.

For Cohort B, futility analysis will be performed when approximately 35 participants are enrolled into the cohort and have at least 2 objective tumor response assessments per independent centralized radiological review or are discontinued from the study or are discontinued from treatment without post-treatment tumor assessments. Cohort B can be stopped for futility if  $\leq 6$  responders are observed in RECIST/RANO evaluable population, for which there is approximately 14% probability of claiming ORR  $> 15\%$  at final analysis. This rule is just a guidance and nonbinding.

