7.1. Efficacy Hypotheses

Objective Response Rate (Primary Endpoint): Administration of pemigatinib to participants in Cohort A and B improves ORR from 15%. Assume ORR_A and ORR_B are the ORRs for cohort A and B respectively.

The hypotheses for Cohort A are as follows:

- H_0 (null hypothesis): $ORR_A \leq 15\%$
- H_A (alternative hypothesis): $ORR_A > 15\%$

The hypotheses for cohort B are as follows:

- H_0 (null hypothesis): $ORR_B \leq 15\%$
- H_A (alternative hypothesis): $ORR_B > 15\%$

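### The futility set is defined by status with no enrolment order or minimum follow-up, so the interim response rate is selected on outcome and the 4/25 and 6/35 rules need not have their binomial false-stop risks

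*Protocol*

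**What the plan says.** Protocol 10.5 ties each futility look to a count of participants who hold a status. The Cohort A trigger reads: "futility analysis will be performed when approximately 25 participants are enrolled into the cohort and have at least 2 objective tumor response assessments" by central review. The Cohort B trigger reads: "futility analysis will be performed when approximately 35 participants are enrolled into the cohort and have at least 2 objective tumor response assessments", again by central review. Participants without two assessments can also count if they "or are discontinued from the study or are discontinued from treatment without post-treatment tumor assessments". Responders are counted in the RECIST/RANO evaluable population, which Table 16 defines by the same status: two central assessments, "or who discontinued from the study or who discontinued from treatment without post-treatment tumor assessments".

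Cohort A may be stopped at 4 or fewer responders and Cohort B at 6 or fewer. The Protocol calls the rule nonbinding guidance.

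SAP 9 and SAP 5.3.4 use the same trigger and population but admit early cases only through study discontinuation; the treatment-discontinuation limb is absent. The SAP was written against Protocol Amendment 2.

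None of these sections refers to the first 25 or 35 enrolled, and none sets a minimum follow-up.

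**The concern.** When a sample is filled by status, and different outcomes reach that status at different speeds, the outcome influences who is in the sample. Here the speeds differ:

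- A participant who leaves before any scan can qualify within weeks.
- A participant who stays on treatment with stable disease needs two 9-weekly scans (Protocol 8.2.1), about 18 weeks.
- A responder needs 18 weeks on the regular schedule. If the optional confirmatory scan is done 4 weeks after a week-9 response, 9 + 4 = 13 weeks.
- A participant who progresses at the week-9 scan has one assessment. If the Protocol's treatment-discontinuation limb means no scan after stopping drug, that participant qualifies on stopping. If it means no scan after baseline, or if the SAP wording applies, the participant enters survival follow-up (Protocol 8.8.3), remains on study, and may qualify much later.

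While the first 25 are qualifying, later enrolees with fast-qualifying outcomes can enter ahead of earlier enrolees still waiting for scans. The interim ORR then no longer estimates the cohort ORR. Because Cohort B is tested only if Cohort A is significant (Protocol 10.3), a mistaken stop of A would also remove the formal test of B.

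**Working it through.** **Inputs from the documents.** "The overall level of significance is 1-sided 0.025" (Protocol 10.3). The null ORR is 15% in both cohorts (SAP 7.1). Cohort A: "Assuming the true ORR is 35% for the intervention in this group, 60 participants are needed". Cohort B: "Assuming the true ORR is 30% for the intervention in this group, 90 participants are needed". The stop limits are 4 of 25 and 6 of 35.

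**Final cut-offs.** The smallest r with P(X ≥ r | N, 0.15) ≤ 0.025:
- A: 16 of 60 (exact alpha 0.0136, power at 35% = 93.4%).
- B: 21 of 90 (exact alpha 0.0240, power at 30% = 93.5%).

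Both meet the stated power of at least 90%.

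**The plan's boundary figures.** The documents do not state the method. A beta-binomial predictive probability with prior Beta(0.35, 0.65) for A and Beta(0.30, 0.70) for B matches:
- A at 4/25 needs 16 − 4 = 12 or more of the remaining 35: 6.1% (stated below 10%).
- B at 6/35 needs 21 − 6 = 15 or more of the remaining 55: 13.9% (stated about 14%).

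This calculation treats the interim count as plain binomial.

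**False-stop risk in an unselected sample.**
- A: P(X ≤ 4 | 25, 0.35) = 0.032.
- B: P(X ≤ 6 | 35, 0.30) = 0.065.

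**False-stop risk when the set is the first 25 or 35 to qualify.** This was simulated. The documents give no accrual or early-stopping rates, so these are assumptions: exponential accrual at 0.25 to 1 participant per week per cohort; 10 to 20% of participants stopping unscanned, qualifying at weeks 2 to 9; everyone else at week 18 unless the row says otherwise.

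| Setting | Cohort A | Cohort B |
|---|---|---|
| Set fixed by enrolment order | 3.2% | 6.5% |
| Responders at week 18 | about 3.5–6.8% | about 6.8–10.7% |
| As above, and 30% progress at week 9 and qualify on stopping | about 4–14% | about 8–17% |
| All responders at week 13, no week-9 route | about 1.6–3.2% | about 4.2–6.3% |
| All responders at week 13, and 30% progress at week 9 and qualify on stopping | about 3–6% | about 6–9% |
| Responders at week 18, and 30% progress at week 9 and qualify late (week 35 assumed) | about 0.8–2.5% | about 2.9–6.0% |

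The departure from the binomial value grows with accrual. At 0.25 per week it is small.

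**Effect on power if the rule were always followed.** With a set fixed by enrolment, power is 91.7% (A) and 89.3% (B). In a separate run at 1 per week, responders qualified at week 18, 20% of non-responders left early, and a further 30% of non-responders progressed at week 9 and qualified by week 12. Power was then 88.1% (A) and 84.3% (B). At 2 per week it was 80.1% and 76.5%.

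**The case against.** A reader might infer that the plan fills the set with early failures, biases the interim ORR downward and so stops active cohorts too often. The documents do not support that as a general statement, for three reasons.

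1. First-to-qualify is inferred from silence. The wording also fits a first block of about 25 who are followed until each is resolved, with the discontinuation limbs there to keep early failures in the denominator.
2. Responders need not wait 18 weeks. SAP 7.2.1 requires confirmation and Protocol 8.2.1 allows the confirming scan after 4 weeks. If every responder uses it and the week-9 route is closed, the risk is at or below the binomial value.
3. The handling of week-9 progressors changes the sign. Under the SAP wording they tend to be left out, which raises the interim ORR.

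Larger figures, up to 39% in Cohort A, can be produced. They need 2 enrolments per week in one cohort, heavy early loss, immediate qualification of every week-9 progressor and no early confirmation. No document supports that combination.

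The consequence is also limited. The rule is nonbinding, the trial is open-label with an internal monitoring committee that can take pending responders into account, and a futility stop does not raise type I error.

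All of this stands against a one-directional claim. It does not answer the narrower point. The optional scan cannot speed up a response first seen at week 18. Protocol 8.8.2 uses post-treatment for the period after stopping drug and schedules imaging there only for those who stopped for reasons other than progression, so entry of week-9 progressors on stopping is a fair reading of the current Protocol. And a rule whose error changes sign with optional scans and accrual does not have known operating characteristics.

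**Conclusion.** The point holds as a defect of definition. The interim set is selected on outcome if the text is followed literally, and the 4/25 and 6/35 limits then need not carry the 3.2% and 6.5% false-stop risks of an unselected sample. Across the settings tried at 0.25 to 1 enrolment per week, the risk lay between about 0.8% and 14% for A and between about 2.9% and 17% for B, on both sides of the binomial values. Direction and size depend on accrual, early stopping, use of the optional scan and the discontinuation limb applied. The first three are unknown, and the Protocol and SAP disagree on the fourth. Where the interim ORR is biased upward, the cost is different: an inactive cohort is less likely to be stopped. The final type I error is not raised, and loss of the Cohort B test would need a discretionary stop of Cohort A. This should be corrected, but it does not invalidate the design.

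**What to change.** Use one identical definition in Protocol 10.5, Table 16, SAP 5.3.4 and SAP 9:

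- The futility set is the first 25 (Cohort A) or 35 (Cohort B) treated participants assigned to the cohort, ordered by date of first dose.
- The look is held when each of them has had two post-baseline central assessments, plus the confirmatory scan if a response is first seen at the second, or has earlier progressed, died or discontinued without further assessments.
- All 25 (35) stay in the denominator. Those lacking a response count as non-responders.

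Membership then does not depend on outcome, so the false-stop risks return to 3.2% and 6.5% in every setting above, and the difference between the Protocol and SAP limbs is resolved. The cost is wording in both documents, a look some weeks later, and a few more participants enrolled before it.

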## **11. SUPPORTING DOCUMENTATION AND OPERATIONAL CONSIDERATIONS**

### **11.1. Investigator Responsibilities**

- The Protocol, Protocol amendments, ICF, IB, and other relevant documents (eg, advertisements) must be submitted to an IRB/IEC by the investigator and reviewed and approved by the IRB/IEC before the study is initiated.
- The investigator is responsible for ensuring that the safety reports provided by the sponsor are reviewed and processed in accordance with regulatory requirements, the policies and procedures established by the IRB/IEC, and institutional requirements.
- Any amendments to the Protocol will require IRB/IEC approval before implementation of changes made to the study design, except for changes necessary to eliminate an immediate hazard to study participants.
- The investigator will be responsible for the following:
  - Providing written summaries of the status of the study to the IRB/IEC annually or more frequently in accordance with the requirements, policies, and procedures established by the IRB/IEC.
  - Notifying the IRB/IEC of SAEs or other significant safety findings as required by IRB/IEC procedures.
  - Providing oversight of the conduct of the study at the site and adherence to GCP, IRB/IEC requirements, institutional requirements, and applicable laws and country-specific regulations.

- Adhering to the Protocol as described in this document and agreeing that changes to the Protocol procedures, with the exception of medical emergencies, must be discussed and approved, first, by the sponsor or its designee and, second, by the IRB/IEC. Each investigator is responsible for enrolling participants who have met the specified eligibility criteria.
- Retaining records in accordance with all local, national, and regulatory laws, but for a minimum period of at least 2 years after the last marketing application approval in an ICH region and until there are no pending or contemplated marketing applications in an ICH region, or if not approved, 2 years after the termination of the test article for investigation to ensure the availability of study documentation should it become necessary for the sponsor or a regulatory authority to review.
  - The investigator must not destroy any records associated with the study without receiving approval from the sponsor. The investigator must notify the sponsor or its designee in the event of accidental loss or destruction of any study records. If the investigator leaves the institution where the study was conducted, the sponsor or its designee must be contacted to arrange alternative record storage options.
  - All eCRF data entered by the site (including audit trail), as well as computer hardware and software (for accessing the data), will be maintained or made available at the site in compliance with applicable record retention regulations. The sponsor will retain the original eCRF data and audit trail.
- For Japan: The record retainer (delegated by head of study site) will retain the J-GCP defined essential documentation at this site until the regulatory approval of study drug(s)/treatment or at least 3 years after the discontinuation or completion of the study conduct, whichever is later. If the sponsor requires retention of these documents for a longer period of time, the duration and method of retention will be decided upon through discussion between the sponsor and the study site. It is the responsibility of the sponsor to inform the head of the study site as to when the documents no longer need to be retained.

## 11.2. Data Management

Data management will be performed in a validated EDC system. The investigator will be provided with access to an EDC system so that an eCRF can be completed for each participant.

The site will be provided eCRF completion guidelines for instructions on data entry in the eCRF. The study monitor will reference the Monitoring Plan in order to ensure that each issue identified is appropriately documented, reported, and resolved in a timely manner in accordance with the plan's requirements.

The sponsor (or designee) will be responsible for:

- The data management of this study including quality checking of the data.

- Ensuring that study monitors perform ongoing source data verification to confirm that data entered into the eCRF by authorized site personnel are accurate, complete, and verifiable from source documents; that the safety and rights of participants are being protected; and that the study is being conducted in accordance with the currently approved protocol and any other study agreements, ICH GCP, and all applicable regulatory requirements.

The investigator will be responsible for:

- Ensuring participant data relating to the study is recorded in the eCRF unless transmitted to the sponsor or designee electronically (eg, laboratory data, diary data) or as otherwise specified in the Protocol. The investigator is responsible for verifying that data entries are accurate and correct by physically or electronically signing the eCRF.
- Maintaining accurate documentation (source data) that supports the information entered in the eCRF.
  - Source documents provide evidence for the existence of the participant and substantiate the integrity of the data collected. Source documents are filed at the investigator's site.
  - Data reported on the CRF or entered in the eCRF that are transcribed from source documents must be consistent with the source documents or the discrepancies must be explained. The investigator may need to request previous medical records or transfer records, depending on the study. Also, current medical records must be available.
- Permitting study-related monitoring, sponsor audits, IRB/IEC review, and regulatory inspections by providing direct access to source data and other relevant clinical study documents.
  - Monitoring: Qualified representatives of the sponsor or its designee, study monitors, will monitor the study according to a predetermined plan. The investigator must allow the study monitors to review any study materials and participant records at each monitoring visit.
  - Auditing: Qualified representatives of the sponsor or its designee may audit the clinical study site and study data to evaluate compliance with the Protocol, applicable local clinical study regulations, and overall study conduct. The investigator must allow the auditors to review original source records and study documentation for all participants.
  - Regulatory inspection: Regulatory authorities may conduct an inspection of the study and the site at any time during the development of an investigational product. The investigator and staff are expected to cooperate with the inspectors and allow access to all source documents supporting the eCRFs and other study-related documents. The investigator must immediately notify the sponsor when contacted by any regulatory authority for the purposes of conducting an inspection.

